#### 9.6 Handling Missing Data

The primary analysis will treat missing data as missing at random then analyze cases with complete data. The method of multiple imputation will be used to handle missing data if more than 20% of the cases have missing data in the variables of interest. If so, sensitivity analysis will be performed to compare results from the complete case analysis and imputation analysis. In case of discrepancies, possible explanations will be discussed. For longitudinal data, given the expected high level of missingness in these data, data will be analyzed according to the methods described in Schluchter (1992) and in Schluchter, Greene, and Beck (2001). These methods take into account the possibility of informative missingness by jointly modeling the longitudinal response and the time to dropout.

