## 9.3 Primary Objective: Efficacy

### *Primary Endpoint—2-year PFS rate*

The sample size calculations are based on the efficacy endpoint of 2-year PFS rate, which is defined as the proportion of patients alive and progression-free at 24 months measured from date of registration onto Step 1. Patients who die without disease progression within 24 months and patients who begin non-protocol therapy without evidence of progression within 24 months will not be considered to be progression-free at 24 months. The 2-year failure proportions that include second primary cancers from the head and neck region as event will also be reported.

The regimen of TOS + low-dose radiation (Arm B and Arm C, separately) may be considered worthy of further study if the true 2-year PFS rate is close to 85% (the observed rate among high-dose radiation patients in E2399).

Assuming 90 analyzable patients per arm for the intermediate group, the following table displays the exact 90% binomial confidence intervals (CIs) for the 2-year PFS rate for each of Arm B and C, assuming various observed 2-year

Rev. 6/14

PFS rate. For example, if 79 out of 90 analyzable patients per arm are alive and progression free at 2 years, the 90% confidence interval will be 81% to 93% with a width of 12%. This study will need 180 analyzable patients in total for the two randomized arms (Arms B + Arm C).

	Number of Alive and Progression Free at 2 Years			
	71	75	79	83
90% CI	(0.71, 0.86)	(0.76, 0.89)	(0.81, 0.93)	(0.86, 0.96)

With regard to p16 status, while central evaluation of pathology reports will be conducted retrospectively, actual assays will not be run or reviewed centrally. Patients who drop-out prior to radiation therapy due to any reason will also be excluded from the primary analysis .

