In the original design, the risk distribution was assumed to be 10% low risk, 60% intermediate risk, and 30% high risk, and an interim analysis for the first 59 patients who complete transoral resection was scheduled. Based on the analysis results, among the 104 evaluable patients (not ineligible based on current evaluation, and started treatment on step 2), the estimated risk distribution is: 8% low risk, 48% intermediate risk and 32% high risk (13 (12%) patients had potentially misclassified risk category/ arm based on their surgical data and the study team is taking various actions trying to improve this). As was stated in the original design, in case the proportion of the intermediate risk patients is off over 5% from the anticipated 60%, the accrual goal would be adjusted, With this new accrual goal, we expect at the end of the study ~180 evaluable patients would be intermediate risk, ~120 high risk, and ~30 low risk.

In analyzing the 2-year PFS rate, 90% exact binomial confidence intervals will be computed for each arm. Only eligible patients with confirmed P16+ status who started radiotherapy will be analyzed (by arm). The regimen will be considered worthy of further study if the higher limit of the computed 90% CI exceeds 85%.

Comparisons of 2-year PFS rates between Arms B and C, Arms B and D, and Arms C and D are exploratory endpoints. Since one of the randomized arms proposed in this study is likely to be selected for a follow-up phase III study, the exploratory comparison of 2-year PFS rate between the two randomized arms is more important and a p-value  $\leq 0.05$  will be considered statistically significant. For the other two comparisons (Arms B and D; Arms C and D), the Type I error rate of 5% will be divided by the two tests (i.e., 0.05/2 considered statistically significant). Therefore, the family-wise error rate of 0.10 will be protected for the multiple comparisons in the 2-year PFS rate among arms. Power for various differences in the 2-year PFS rate is shown below, assuming a two-sided Fisher's exact test and 90 analyzable patients in Arms B or C, and 120 analyzable patients in arm D.

Difference in 2-year PFS rate between arms	Arm C vs. Arm B	Arm B (or C) vs. Arm D
10% (85% vs. 75%)	0.32	0.27
15% (85% vs. 70%)	0.62	0.58
20% (85% vs. 65%)	0.85	0.83
25% (85% vs. 60%)	0.96	0.96

*Interim Analysis—1-year PFS rate*

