## 9.5 Secondary Objectives

Secondary endpoints include toxicity, overall survival, swallowing function, and patient-reported outcomes.

*Toxicity.* For each arm, all treated patients (regardless of eligibility) will be evaluated by CTCAE version 4.0. Descriptive statistics will be provided (by arm). Difference between the low-dose RT arm (Arm B and Arm C separately) and Arm D and between Arm B and Arm C will be evaluated using Fisher's exact test.

*Overall Survival.* Overall survival will be determined as the time from registration onto the study until death from any cause. Patients who were alive at the time of analysis will be censored at the date last known alive. Kaplan-Meier estimates will be calculated, along with their corresponding 95% confidence intervals. The median, 1-year, and 2-year survival rates will be estimated. Only eligible and treated patients will be analyzed for overall survival (by arm).

*Swallowing Function and Voice.* Descriptive statistics will be provided (by arm) for swallowing function, evaluated using the MBS ratings, PSS-HN normalcy of diet scale, and the validated survey MDADI instrument. Longitudinal analysis will be performed, by arm, on each of these measures. All eligible and treated patients (on both steps) will be analyzed for PSS-HN diet scale, MDADI, and VHI-10. The MBS analysis will be performed on eligible and treated patients only if accrued at vetted participating centers.

*Quality of Life.* The primary variable of interest in the QOL analysis is the individual change in the FACT-H&N total score from baseline (prior to TOS) to 6 months post-RT. Patient QOL will be grouped as "improved" (change  $\geq 7$  points, 6 mo post-RT vs. baseline), "worsened" (change  $\leq -7$  points) and "stable" ( $-6 \leq \text{change} \leq 6$ ). QOL data is very limited in this setting (P16+ OPSCC patients treated with TOS + RT), and estimates from this phase II trial may serve as the basis of choosing an effect size in a possible future phase III trial comparing TOS + RT vs. primary CRT treatment.

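### The 2-year PFS proportion has no censoring rule, and the default complete-case rule gives a modest downward bias that Kaplan-Meier would remove

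*Combined protocol and SAP*

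**What the plan says.** Section 9.3 defines the primary efficacy endpoint as "the proportion of patients alive and progression-free at 24 months measured from date of registration onto Step 1". Deaths without progression within 24 months are failures. So are starts of other treatment: "patients who begin non-protocol therapy without evidence of progression within 24 months will not be considered to be progression-free at 24 months". There is no corresponding rule for a patient who is event-free at last contact before 24 months.

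The analysis is binary: "In analyzing the 2-year PFS rate, 90% exact binomial confidence intervals will be computed for each arm". The design figure is introduced by "Assuming 90 analyzable patients per arm for the intermediate group", and the decision rule is "The regimen will be considered worthy of further study if the higher limit of the computed 90% CI exceeds 85" (per cent).

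Section 9.6 is general and does not mention PFS. It says "The primary analysis will treat missing data as missing at random then analyze cases with complete data". Multiple imputation, with a comparison against the complete-case result, follows only if more than 20% of cases have missing data.

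For overall survival, Section 9.5 does state a censoring rule (date last known alive) and an estimator: "Kaplan-Meier estimates will be calculated, along with their corresponding 95% confidence intervals". Neither is stated for PFS. The accrual target in Section 9 (180/0.35 = 515) allows for patients who are ineligible or do not start Step 2, but not for later loss to follow-up.

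**The concern.** A patient who progresses at month 3 and is then lost has a known 24-month status. A patient who is event-free at month 20 and is then lost does not. Whether a case is complete therefore depends on its outcome. A complete-case proportion keeps every observed failure and removes some of the successes, so it is too low even when loss has nothing to do with prognosis. It also discards up to 24 months of event-free follow-up from each lost patient.

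At stake are the accuracy and precision of the per-arm primary estimate. It is read against 85%, and it would inform which randomized arm goes forward to phase III.

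**Working it through.** **The plan's own figures.** Exact (Clopper-Pearson) 90% intervals for 71, 75, 79 and 83 of 90 are (0.706, 0.857), (0.755, 0.894), (0.806, 0.930) and (0.859, 0.963). They agree with the table in Section 9.3. At 70/90 the upper limit is 0.848 and at 71/90 it is 0.857, so with 90 patients the rule passes from 71 (78.9%).

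**Inputs.** From Section 9.3: n = 90 per arm and a true 2-year PFS of S = 0.85. Assumed, because the documents give no figure: a probability d of loss by 24 months of 5%, 10% or 20%, independent of prognosis, with exponential event and loss times.

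**Formulas.** With 24 months as the time unit, λ = -ln S and γ = -ln(1-d).

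- Followed and event-free at 24 months: A = S(1-d).
- Failure observed before any loss: B = [λ/(λ+γ)](1-A).
- Expected complete-case estimate: q = A/(A+B).
- Expected analysed number: 90(A+B).

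For S = 0.85 and d = 0.10: λ = 0.1625, γ = 0.1054, A = 0.765, B = 0.6067 × 0.235 = 0.1426, and q = 0.765/0.9076 = 0.843.

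| Assumed loss | A | B | Analysed n | Expected estimate | Bias (points) | Complete-case variance vs Kaplan-Meier (simulated) |
|---|---|---|---|---|---|---|
| 5% | 0.8075 | 0.1463 | 85.8 | 84.7% | -0.3 | +4% |
| 10% | 0.7650 | 0.1426 | 81.7 | 84.3% | -0.7 | +8% |
| 20% | 0.6800 | 0.1348 | 73.3 | 83.5% | -1.6 | +18% |

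In the same simulated trials the Kaplan-Meier estimate averaged 85% at every loss rate. At a true 80% the bias is -0.4, -0.9 and -2.0 points.

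**Sensitivity to timing.** Suppose all loss falls at month 20. Then S(20) = 0.85^(20/24) = 0.873, and the estimate is 0.85(1-d)/[0.873(1-d) + 0.127]. The bias becomes -0.6, -1.2 and -2.6 points.

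**Decision rule.** The probability of passing is the sum over m of P(m analysed of 90, each with probability A+B) × P(at least x_m successes of m, each with probability q). Here x_m is the smallest count whose exact upper limit exceeds 0.85. The Kaplan-Meier column uses a 90% log(-log) Greenwood interval and is simulated. True rate 85%:

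| Assumed loss | Complete case, exact interval | Kaplan-Meier, log(-log) interval |
|---|---|---|
| none | 0.957 | 0.956 |
| 5% | 0.956 | 0.939 |
| 10% | 0.944 | about 0.94 |
| 20% | 0.921 | 0.942 |

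Simulation of the complete-case column agrees within about 0.005.

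**The other literal reading.** If lost patients stay in the denominator as not progression-free, the expected estimate is A: 80.8%, 76.5% and 68.0%. The probability of passing, P(Bin(90, A) ≥ 71), is 0.73, 0.35 and 0.02.

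**The case against.** - **Attribution.** Section 9.6 is generic, and Section 9.3 sets the analysis population (eligible, p16 confirmed, radiotherapy started) without excluding patients lost later. That the plan drops them is an inference. This stands as a caveat. But 9.6 is the only rule that reaches these patients, and the alternative reading is biased further in the same direction.
- **Decision.** A reader might infer that a bias of even one point threatens the comparison with 85%, or that the smaller n loosens the rule. The documents do not support either. The rule uses the upper 90% limit, not the point estimate. The downward bias lowers that limit and the smaller n raises it, so the two largely offset at 5-10% loss.
- **Scale.** The loss rates are assumed. Follow-up is dense: visits every 3 months for two years, imaging every 6 months for three years, survival to 5 years. A later event-free assessment settles a missed one, so only permanent loss counts. The 20% scenario leaves about 18.5% missing, just under the imputation trigger, so under uniform loss -1.6 points is near the ceiling for complete-case analysis alone at a true 85%.
- **Direction.** Informative loss could reverse the sign, and Kaplan-Meier also assumes independent censoring. This stands.
- **Cost of the fix.** At 71/90 with no loss, the log(-log) upper limit is 0.8501 against 0.8571 exact, about 0.7 points lower and right at the pass boundary. This stands and shapes the fix.

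A landmark proportion with an exact interval is a recognised phase II choice. That does not remove the need to say what happens to patients whose landmark status is unknown.

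**Conclusion.** The concern holds as a modest, avoidable weakness in the primary estimate. Following Section 9.6 as written gives an expected shortfall of about 0.3, 0.7 and 1.6 points at 5%, 10% and 20% assumed loss, with a true rate of 85%, and a less precise estimate than Kaplan-Meier would give. This rests on loss unrelated to prognosis and on assumed loss rates. Later loss makes the bias larger, and informative loss could turn it around.

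It does not show that the go/no-go decision is compromised. The probability of passing at a true 85% barely moves at 5-10% loss, and a gain from Kaplan-Meier appears only near 20% (0.921 against 0.942). The larger exposure is the silence itself: counting lost patients as failures would change the probability of passing from about 0.94 to 0.35 at 10% loss, and nothing in Section 9.3 rules that reading out.

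**What to change.** In Section 9.3, estimate 2-year PFS per arm by Kaplan-Meier from Step 1 registration. Count progression, death and start of non-protocol therapy as events, as the section already does, and censor event-free patients at their last disease assessment. Report a 90% interval. Keep the exact binomial proportion as a supportive analysis; the two point estimates coincide if nobody is lost before 24 months. State that Section 9.6 does not govern this endpoint.

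Because the log(-log) limit is about 0.7 points below the exact one near 71/90, name the interval that feeds the 85% rule and restate the rule's operating characteristics under it, including at 5% loss, where the probability of passing at a true 85% falls from 0.956 to 0.939.

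The cost is a short edit to the statistical section and standard software, with no new data. The price is an asymptotic interval in place of an exact one.

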#### 5.1.19 Patient Reported Outcomes (PROs)

Quality of Life (QOL) assessments will be performed at baseline, end of treatment, and at 3, 6, 12, and 24 months after completion of treatment. If an additional tumor assessment is done prior to 3 years from study entry, one final QOL assessment is requested. Please refer to Appendix V for the complete schedule.

QOL will continue to be collected for all patients post recurrence.

Paper questionnaires will be completed by the patient, and then data from the questionnaire should be entered into Medidata Rave within 7 days of completion. The original copy needs to be kept in the study subject's research binder. Refer to the ECOG website for a copy of the questionnaire.

Rev. 6/14

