In the primary QOL analysis, we plan to combine the post-operative RT arms (B & C) and compare to patients selected for post-operative chemoRT (arm D), which would be expected to have toxicity similar to, but less severe than, a primary CRT approach. This comparison is most similar to the setting of a possible future phase III trial. From a prior trial of CRT approach, about 25% of the patients had improved FACT-H&N from baseline to 6 months, 25% were stable, and 50% worsened, which is expected to be similar to, or slightly worse than the experience of arm D in this phase II trial. Given the more severe overall toxicity and probable greater late toxicity associated with the use of both radiation and chemotherapy, we hypothesize that a higher proportion of patients in arm B/C will have recovered their FACT-H&N scores to baseline level or higher at 6 months, and we consider a difference, or Delta, of 10% (Arms B/C vs. Arm D) to be important outcome. Comparison between Arm B and Arm C (in mean score change and/or proportion of patients with improved/stable score at 6 months) is also important endpoint but this will be only exploratory. Any comparison results will be interpreted with caution. Descriptive statistics will be provided for FACT-H&N and MDASI-HN at various measurement points.

The table below shows the power of detecting various Delta value (Arms B/C vs. D) under various compliance rate (the proportion of patients who complete PRO surveys at both baseline and 6 months post-RT visits), using a one-sided Fisher's exact test with type I error rate of 0.10, assuming 48% intermediate risk patients and 32% high risk patients among evaluable patients.

Compliance Rate	No. of analyzable pts (Arms B/C vs. Arm D)	Delta (Arms B/C vs. D)		
		10% (65% vs. 55%)	15% (70% vs. 55%)	20% (75% vs. 55%)
40%	120 (72 vs. 48)	0.35	0.58	0.79
60%	180 (108 vs. 72)	0.46	0.73	0.91
80%	240 (144 vs. 96)	0.56	0.83	0.96

One of the randomized arms is likely to be selected for a future phase III study. Although the QOL endpoint is not built into the primary selection criteria, in case that the efficacy outcomes for the two randomized arms are similar, the 50Gy schedule will be considered in the phase III study with the expectation that QOL will also be better in this arm, unless there is evidence otherwise.

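### Section 9.6 assumes data are missing at random but makes complete cases the primary analysis, so each arm's 6-month FACT-H&N rate can be biased, and the imputation rule does not settle which result counts

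*Combined protocol and SAP*

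**What the plan says.** Section 9.6 sets the default: "The primary analysis will treat missing data as missing at random then analyze cases with complete data". It brings in multiple imputation "if more than 20% of the cases have missing data in the variables of interest", and in that event "sensitivity analysis will be performed to compare results from the complete case analysis and imputation analysis". If the two disagree, explanations are to be discussed. For longitudinal data, "given the expected high level of missingness in these data", it turns to "jointly modeling the longitudinal response and the time to dropout".

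The primary quality-of-life variable in Section 9.5 is each patient's change in FACT-H&N total score from baseline to 6 months post-RT, grouped as improved, stable or worsened. Arms B and C are pooled and compared with Arm D by a one-sided Fisher's exact test at 0.10. The power table is indexed by compliance of 40%, 60% and 80%, defined as "the proportion of patients who complete PRO surveys at both baseline and 6 months post-RT visits". Section 9.5 adds that "estimates from this phase II trial may serve as the basis of choosing an effect size in a possible future phase III trial".

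Other FACT-H&N forms exist between those two visits. Section 5.1.19 says "assessments will be performed at baseline, end of treatment, and at 3, 6, 12, and 24 months after completion of treatment", and Appendix V adds a form 4 to 6 weeks after surgery.

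**The concern.** Missing at random allows return of the 6-month form to depend on scores already observed, such as the 3-month score. If it does, patients with complete data are a selected group and their unadjusted recovery rate is biased. The rate is safe only under the stronger condition that return is unrelated to the 6-month outcome within each arm. The plan states the weaker assumption and uses the method that needs the stronger one.

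The scores that could correct this are scheduled, but the planned two-visit comparison does not use them. Section 9.5 calls a 10-point difference important and may use these estimates to set a phase III effect size, so a bias of several points in an arm's rate matters.

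**Working it through.** **1. The plan's own figures.** Exact enumeration of the one-sided Fisher's test at 0.10 reproduces all nine power values. For true rates of 65%, 70% and 75% against 55%:

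- 72 vs 48 patients: 0.353, 0.575, 0.786 (plan 0.35, 0.58, 0.79)
- 108 vs 72: 0.463, 0.731, 0.912 (plan 0.46, 0.73, 0.91)
- 144 vs 96: 0.556, 0.829, 0.964 (plan 0.56, 0.83, 0.96)

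The sample sizes are compliance times about 180 (B+C) and 120 (D): for example 0.8 × 180 = 144 and 0.8 × 120 = 96. The table therefore counts complete cases only and assumes equal compliance in the two groups.

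**2. When imputation starts.** Missing = 1 − compliance, which is 60%, 40% and 20% in the three scenarios. The trigger is more than 20%. Imputation runs at 40% and 60% compliance, but not at exactly 80%.

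**3. Size of the bias.** True rates of 65% and 55% come from the plan's table. The rest is assumed, because the documents give no values: a correlation ρ = 0.7 between the 3- and 6-month changes, and an odds ratio (OR) of 1.5 to 3 for returning the 6-month form per SD of the 3-month change. Let z be the standardised 3-month change in an arm, p the true rate and c the compliance.

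- Return: r(z) = 1 / (1 + exp(−(a + ln(OR)·z))), with a chosen so that r averages c.
- Recovery: P(z) = Φ((ρz + Φ⁻¹(p)) / √(1 − ρ²)).
- Complete-case rate = average of r(z)·P(z), divided by c.

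Results with equal compliance in both groups (B+C / D, %; difference taken before rounding):

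| Compliance | OR 1.5 | OR 3 | Difference at OR 3 | OR 1/1.5 (better patients drop out) |
|---|---|---|---|---|
| 80% | 67.1 / 57.2 | 70.2 / 60.3 | 9.9 | 63.0 / 52.8 |
| 60% | 69.1 / 59.4 | 74.6 / 65.2 | 9.5 | 61.0 / 50.7 |
| 40% | 71.0 / 61.5 | 78.8 / 70.0 | 8.8 | 58.8 / 48.5 |

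At 80% compliance the excess is 67.1 − 65 = 2.1 to 60.3 − 55 = 5.3 points. If both groups share one return curve, so that Arm D, with worse scores, also returns fewer forms, Arm D reaches about 61%, an excess of about 6. With ρ = 0.5 the bias is smaller but has the same sign.

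**4. Different mechanisms in the two groups, 80% compliance.** OR 3 in D only: 65.0 − 60.3 = 4.7 points. OR 3 in B+C only: 70.2 − 55.0 = 15.2 points. The true difference is 10.

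**5. Sampling error at 80% compliance, for scale.** B+C: √(0.65 × 0.35 / 144) = 4.0 points. D: √(0.55 × 0.45 / 96) = 5.1 points. Difference: √(4.0² + 5.1²) ≈ 6.4 points.

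**The case against.** The plan does not stop at complete cases. Above 20% missing, Section 9.6 makes imputation a handling method and requires the two results to be compared. The largest figures above, at 60% and 40% compliance, therefore describe an analysis that would not stand alone. This part of the objection stands. What remains is that the plan does not say which result is then primary, what decides if they disagree, or whether earlier FACT-H&N scores enter the imputation model.

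The joint response-dropout models are assigned to longitudinal data and are not limited to swallowing. However, Section 9.5 names longitudinal analysis only for the swallowing and voice measures, and plans descriptive statistics for FACT-H&N at its several visits. Whether the joint models reach FACT-H&N is unclear, and they do not evidently cover a Fisher's test at one time point.

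A reader might infer that the plan overstates recovery. The documents do not support that: nothing says who fails to return forms, and the last column of the table shows the opposite error. Section 5.1.19 also continues collection after recurrence, which closes one route to selective loss.

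A reader might also infer that the B+C versus D difference shrinks materially. With the equal compliance of the plan's own table, the loss at 80% is about 0.1 point against a standard error of 6.4. Larger shrinkage comes mainly from assuming lower compliance in Arm D.

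Finally, this is a secondary, non-randomised comparison of different risk groups, and Section 9.5 itself advises caution.

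**Conclusion.** The mismatch between assumption and method is real and worth correcting. With 20% or less missing, the plan offers only a complete-case rate, which can be biased when return depends on intermediate scores. Above 20% it leaves the primary result and the imputation model open.

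At 80% compliance the error in each arm's rate is about 2 to 6 points, upward if patients doing worse drop out and downward if patients doing better do. That is similar in size to each rate's standard error of 4 to 5 points. It rests on the assumed correlation of 0.7 and odds ratios of 1.5 to 3; the direction is not in the documents.

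The difference between groups is nearly unchanged under a common mechanism with equal compliance. It can be pushed either way when these differ by group (4.7 or 15.2 points instead of 10 in the example). The documents do not support a claim that the earlier forms are ignored at every level of missingness, or that recovery is necessarily overstated. The 2-year PFS analysis is not affected.

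**What to change.** In Sections 9.5 and 9.6, make multiple imputation the primary quality-of-life analysis whatever the percentage missing. Impute the 6-month FACT-H&N score from arm, baseline, post-surgery, end-of-RT and 3-month FACT-H&N scores. Classify each completed data set as improved, stable or worsened, then pool the two groups' improved-or-stable rates and their difference. Report complete cases as the sensitivity analysis. A mixed model on all visits could support mean change, but does not directly give the planned responder proportion.

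The cost is SAP wording and slightly more analysis, with no new data. The result will rely on an imputation model, and it gains least for patients who stopped returning forms before 3 months.
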